5.1 Data and Protocol Management

A standard procedure to ensure participant confidentiality will be established. Personal identification information will be kept confidential and will be available only to the PI and relevant study staff. The study database will also be kept confidential and will be password protected. The results of this study will be reported by group results only and no individual results will be reported.

5.2 Safety Monitoring

In addition, a safety monitoring rule will be implemented using the method of Thall, Simon and Estey (1995, 1996). We define the adverse event (AE) as “the percent reduction in BMD is greater than or equal to 15% from baseline to 6 months” and denote its probability as p. The trial will be stopped if, for any arm, there is more than 95% chance that p is greater than 30%, ie, stop the trial if $\text{Prob}(p > 20\% \mid \text{data}) > 0.95$. For each arm, assuming a beta (1, 1) prior and applying the above stopping rule when every 10 patients have been treated and evaluated after 1-year follow-up, the stopping boundaries are as follows: The trial will be stopped if for any one of the two arms, $[\# \text{ patients with AE}] / [\# \text{ patients evaluated at 6 months}] \geq 6/10, 10/20, 14/30, 17/40, 21/50, 24/60$.

Osteonecrosis, primarily in the jaw, has been reported in patients treated with bisphosphonates. Most cases have been in cancer patients undergoing dental procedures, but some have occurred in patients with postmenopausal osteoporosis or other diagnoses. All patients will have dental screening for jaw osteonecrosis at baseline and every 6 months thereafter. Patients with recent tooth extraction and signs of incomplete healing and/or uncontrolled infection will be excluded. During the trial, any dental condition should be treated immediately but conservatively, avoiding any invasive surgical procedure.

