5.0 Statistical Consideration

This is a randomized phase III trial to determine whether the use of Ibandronate significantly decreases the amount of bone loss in patients with BMT, compared to those in the control group. Patients will be equally randomized to control or treatment groups at baseline. All transplant patients will receive oral calcium 500 mg and vitamin D 400 IU twice daily throughout the trial.

The primary endpoint is the percent reduction in bone mineral density (BMD) of the lumbar spine, femoral neck, and total hip measured at 12 month relative to baseline, which we denote here as Diff_BMD. Assuming that the mean Diff_BMD is 12% decrease in the control group and is 0.1% in the treatment (Ibandronate) group, a maximum of 120 patients (60 patients per group)

will be needed in order to have an 80% power to detect this difference at a two-sided significance level of 0.05, assuming a common standard deviation of 0.23. Assuming a drop-out rate of 40% for the patients due to mortality and relapse in the first year, a maximum of 200 patients will be enrolled into the study. The total accrual period will be 20 months, with 10 patients enrolled per month.

Two interim analyses are planned for the primary endpoint of the percent reduction in BMD between baseline and 12 months, when 40 and 80 patients have been accrued into the study and followed for one year, respectively. A Lan-DeMets spending function with O'Brian-Fleming stopping boundaries has been assumed. The two-sided Z-score cut-off values for rejecting the null hypothesis are ± 3.71 and ± 2.51 for the two interim looks, respectively.

The change of BMD between baseline and 12 months will be summarized by treatment and control groups. Data will be transformed as appropriate to satisfy the normality assumption. A two-sample t-test on the transformed data or Wilcoxon rank-sum test will be performed to compare the two groups in terms of percent change of BMD from baseline to 12 months.

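### Section 5.2 states the safety stopping threshold as 30% in words and 20% in the formula; the printed boundaries follow 30%, so formula and boundaries give different stopping decisions

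*Combined protocol and SAP*

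**What the plan says.** Section 5.2 defines the monitored event as "the percent reduction in BMD is greater than or equal to 15% from baseline to 6 months" and calls its probability p. The rule is then given three times.

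- **In words:** the trial stops if, for any arm, "there is more than 95% chance that p is greater than 30%, ie, stop the trial if" the formula that follows.
- **As a formula:** the posterior probability that p exceeds 20% is above 0.95.
- **As a list of boundaries** (patients with the event over patients evaluated, stop at or above): "6/10, 10/20, 14/30, 17/40, 21/50, 24/60".

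The list is presented as the result of the rule: "For each arm, assuming a beta (1, 1) prior and applying the above stopping rule" at every tenth patient per arm. The last entry, 60, agrees with section 5.0, which plans for "a maximum of 120 patients (60 patients per group". The threshold for p is stated nowhere else in the document.

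**The concern.** The connecting *ie* presents the formula as a restatement of the words, but the two carry different thresholds. They cannot both be the rule, and the boundary list can follow from only one of them.

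The rule is binding, and either arm crossing it ends the whole trial. A statistician who programs the formula and one who reads off the list would act differently on the same data. The conflict would surface at an interim look, with results in hand, which is the situation that a pre-specified rule is meant to prevent.

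**Working it through.** **Inputs, all from section 5.2 except where noted.** Prior Beta(1,1) in each arm; posterior cut-off 0.95, the same in words and formula; looks at n = 10, 20, 30, 40, 50 and 60 per arm (60 also from section 5.0); thresholds c = 0.30 (words) and c = 0.20 (formula).

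**Formula.** With x events in n patients, p given the data follows Beta(1 + x, 1 + n − x). The boundary at each look is the smallest x with P(p > c | data) > 0.95.

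**Step 1: reproduce the printed list.** At c = 0.30:

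| n | Printed boundary | P(p > 0.30) at boundary | P(p > 0.30) at one event fewer |
|---|---|---|---|
| 10 | 6 | 0.978 | 0.922 |
| 20 | 10 | 0.974 | 0.932 |
| 30 | 14 | 0.976 | 0.947 |
| 40 | 17 | 0.959 | 0.921 |
| 50 | 21 | 0.968 | 0.941 |
| 60 | 24 | 0.956 | 0.925 |

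Every printed boundary exceeds 0.95, and one event fewer never does. The list is exactly the 30% rule.

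**Step 2: apply the formula as printed.** At c = 0.20:

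| n | Boundary at 20% | Printed boundary | Difference | Counts with opposite decisions |
|---|---|---|---|---|
| 10 | 5 | 6 | 1 | 5 |
| 20 | 7 | 10 | 3 | 7–9 |
| 30 | 10 | 14 | 4 | 10–13 |
| 40 | 13 | 17 | 4 | 13–16 |
| 50 | 15 | 21 | 6 | 15–20 |
| 60 | 17 | 24 | 7 | 17–23 |

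The printed counts do satisfy the 20% criterion, but they are not the smallest counts that do. One event below each printed boundary, P(p > 0.20) is already between 0.988 and 0.9996.

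**Step 3: could another setting rescue 20%?** Cut-offs of 0.90, 0.95, 0.975, 0.99, 0.995 and 0.999 were each tried with six priors, including Beta(1,1), Beta(0.5,0.5) and Beta(0.2,0.8). None gives the printed list at a 20% threshold.

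**Step 4: consequence for stopping.** Exact probability that one arm crosses at any of the six looks, by adding binomial batches of 10 patients and removing the paths that have already stopped:

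| True p | Printed list | 20% formula |
|---|---|---|
| 0.10 | 0.02% | 0.4% |
| 0.15 | 0.2% | 3.5% |
| 0.20 | 0.9% | 16.2% |
| 0.25 | 4.0% | 43.5% |
| 0.30 | 14.2% | 73.7% |
| 0.40 | 64.6% | 98.5% |

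**Step 5: where might p lie?** The document gives no 6-month planning figures. As an illustration only, assume normality and carry the 12-month figures in section 5.0 (mean losses of 0.1% on ibandronate and 12% on control, SD 0.23) back to 6 months.

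- Ibandronate: z = (0.15 − 0.001)/0.23 = 0.648, so p is about 0.26. The arm stops with probability 5% under the list and 49% under the formula.
- Control: z = (0.15 − 0.12)/0.23 = 0.130, so p is about 0.45. The arm stops with probability 86% under the list and 99.8% under the formula.

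**The case against.** The strongest reply is that the list is what monitoring staff would use. It is explicit and needs no posterior calculation. The words and all six boundaries agree, and a single number in the formula differs, which is what a typing slip would look like. On that view the rule works as it stands and the point is editorial.

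A slip is plausible, but the document does not say that the list takes precedence. It derives the list from the rule in the preceding sentence, and that sentence is the one that contradicts itself. The list also covers only six exact counts. If a look falls at 23 evaluable patients, the statistician must go back to the stated rule and will find two thresholds.

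A second reply is that the gap depends on the true p. That is correct. At 0.15 or below both rules seldom stop an arm. At the control rate in the illustration both very probably stop it by 60 patients, so the difference there is more in when than in whether. The gap is widest between about 0.20 and 0.40, and the illustrative ibandronate rate of 0.26 lies in that range.

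**Conclusion.** The concern holds. One sentence gives two thresholds, the printed boundaries are exactly those of the 30% rule, and the 20% formula yields lower boundaries at every look, by 1, 3, 4, 4, 6 and 7 events. For a true p of 0.20 to 0.30, one arm's chance of stopping differs from 0.9% versus 16.2% up to 14.2% versus 73.7%.

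The boundary comparison rests only on the prior, cut-off and look sizes in section 5.2. The stopping probabilities further assume independent patients, a constant p, and looks at exactly 10, 20, up to 60 patients per arm. Because a binding decision threshold is ambiguous, this must be fixed. The documents do not establish which threshold was intended.

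**What to change.** Make the words, the formula and the boundaries in section 5.2 carry one threshold. The choice belongs to the sponsor and the clinical team.

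- **If 30% is intended:** change the formula to P(p > 30% | data) > 0.95. The words and the list can stay.
- **If 20% is intended:** change the words, and replace the list with 5/10, 7/20, 10/30, 13/40, 15/50, 17/60.

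In either case, state which expression governs when a look falls between the listed sample sizes, and add a short table of stopping probabilities for the rule that is kept. The same passage times the looks "when every 10 patients have been treated and evaluated after 1-year follow-up", while the event and its denominator are defined at 6 months; that should be reconciled in the same edit.

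The core correction is one line, or one line and a new list; the operating characteristics add a small table. No patients, visits or procedures are added.

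### Section 5.2 gives two incompatible evaluation times, 6 months and 1 year, for one BMD stopping rule; under the 1-year wording every look comes 6 months after the event is known

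*Combined protocol and SAP*

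**What the plan says.** Section 5.2 (Safety Monitoring) of the combined protocol and SAP makes three statements about time for a single Bayesian rule, applied to each arm separately.

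- The event is "the percent reduction in BMD is greater than or equal to 15% from baseline to 6 months".
- The rule is put into effect by "applying the above stopping rule when every 10 patients have been treated and evaluated after 1-year follow-up".
- The boundaries are counts of events over "patients evaluated at 6 months", namely "6/10, 10/20, 14/30, 17/40, 21/50, 24/60".

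The boundaries are derived "assuming a beta (1, 1) prior". The threshold is given in words as "more than 95% chance that p is greater than 30" percent, while the formula in the same sentence has 20%.

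Section 4.0 and Table 1 schedule DEXA at baseline, 6 and 12 months for both groups. Section 5.0 gives the pace of enrolment: "The total accrual period will be 20 months, with 10 patients enrolled per month". It also says that "a maximum of 200 patients will be enrolled into the study", equally randomized, with an assumed first-year drop-out of 40% from mortality and relapse. No section mentions a pause in accrual before a look.

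**The concern.** The event can be read off the 6-month scan, and the denominator counts patients at 6 months, but the sentence that says when to look refers to 1-year follow-up. Two teams working from this text could hold the first look six months apart. A rule that can stop the trial should not leave that open.

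Two things are at stake if the 1-year wording is followed. First, more patients are enrolled before the rule can act, and the later looks can no longer limit enrolment. Second, it becomes unclear who is counted: a patient with a 6-month scan who is lost before month 12 belongs to the stated denominator, but might not be regarded as evaluated after 1 year.

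A related gap is that the boundaries end at 60 per arm. Sixty per arm is the number expected to complete 12 months. Up to 100 per arm are enrolled, so more than 60 may have a 6-month scan.

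**Working it through.** **1. Reproduce the stated boundaries.** With a beta(1,1) prior and x events in n patients, the posterior is Beta(1+x, 1+n−x). The boundary is the smallest x with P(p > p0 | data) > 0.95.

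| n per arm | Stated | p0 = 0.30 (posterior probability) | p0 = 0.20 |
|---|---|---|---|
| 10 | 6 | 6 (0.978) | 5 |
| 20 | 10 | 10 (0.974) | 7 |
| 30 | 14 | 14 (0.976) | 10 |
| 40 | 17 | 17 (0.959) | 13 |
| 50 | 21 | 21 (0.968) | 15 |
| 60 | 24 | 24 (0.956) | 17 |

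All six stated boundaries match the 30% threshold and none matches 20%. The derivation does not depend on calendar time, so it does not show which evaluation time was intended.

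**2. Timing of the looks.** The inputs, all from Section 5.0, are 10 patients per month, equal allocation (hence 5 per arm per month), a maximum of 200, and drop-out d of 0 or 0.40. Follow-up is counted from enrolment.

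Month of look = n / (1 − d) / 5 + F, with F = 6 or 12. Number enrolled = min(200, 10 × month).

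First look, n = 10:
- d = 0: 10/5 = 2, so 2 + 6 = month 8 (80 enrolled, 40%) against 2 + 12 = month 14 (140 enrolled, 70%).
- d = 0.40: 10/0.6/5 = 3.3, so month 9.3 (93 enrolled, 47%) against month 15.3 (153 enrolled, 77%).

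All looks, as month (number enrolled):

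| n per arm | d = 0, 6 months | d = 0, 1 year | d = 0.40, 6 months | d = 0.40, 1 year |
|---|---|---|---|---|
| 10 | 8 (80) | 14 (140) | 9.3 (93) | 15.3 (153) |
| 20 | 10 (100) | 16 (160) | 12.7 (127) | 18.7 (187) |
| 30 | 12 (120) | 18 (180) | 16 (160) | 22 (200) |
| 40 | 14 (140) | 20 (200) | 19.3 (193) | 25.3 (200) |
| 50 | 16 (160) | 22 (200) | 22.7 (200) | 28.7 (200) |
| 60 | 18 (180) | 24 (200) | 26 (200) | 32 (200) |

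At equal drop-out the difference is 12 − 6 = 6 months at every look, or 6 × 10 = 60 more patients enrolled before the first one. Accrual ends at month 20. Under the 1-year wording the looks at or after that point are those from 40 per arm (d = 0) or from 30 per arm (d = 0.40). Under 6-month timing there are none (d = 0), or only those at 50 and 60 per arm (d = 0.40).

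**3. Sensitivity to the time origin.** Section 4.0 counts the scans from transplant, and Section 1.0 puts the start of treatment at 21 to 60 days after it. With entry at day 21 to 60 and follow-up counted from transplant, the first look has 60 to 86 enrolled (30–43%) at 6-month timing and 120 to 146 (60–73%) at 1 year, over both drop-out values. The lag is still 6 months. Some later looks then move just inside accrual: with entry at day 60 and no drop-out, the 40-per-arm look under the 1-year wording falls at month 18 and the 50-per-arm look at month 20.

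**4. Boundaries beyond 60.** Under the rule in step 1 with p0 = 0.30, the list continues as 28/70, 31/80, 35/90, 38/100.

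**The case against.** The strongest reply is that the 1-year phrase may be a drafting slip. Two of the three timing statements say 6 months, and if the denominator governs, the delay disappears. That stands. It is why the point is an internal contradiction, and why the timings above are conditional on the 1-year wording. It does not remove the need to reconcile the text, because nothing elsewhere settles the matter.

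Three stronger readings are tempting, and the documents do not support them.

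- *A reader might infer that the plan applies the rule only after 1 year.* The text does not say so; it says both.
- *A reader might infer that the rule acts after accrual and most dosing and so cannot protect patients.* This is untrue of the early looks. Under the 1-year wording, looks 1 to 3 (no drop-out) or 1 and 2 (40% drop-out) precede month 20. With no drop-out and the first dose at entry, the ibandronate doses given by month 14 are 5 × (14 + 11 + 8 + 5) = 190 of 100 × 4 = 400, or 48%. The rule would be weakened, but it would still have some effect.
- *A reader might infer that patients lost between months 6 and 12 are dropped and the event rate is therefore understated.* No section says they are dropped, and the stated denominator would include them. Even if they were dropped, no figure in the documents shows whether they lose more or less bone. A delay longer than 6 months appears only if drop-out is applied to the 1-year looks and not to the 6-month looks, which rests on the same unproven exclusion.

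It can also be said that ending the boundaries at 60 per arm agrees with the planned number of completers. That is fair for 12-month data. It is less so for a 6-month event, although the documents give no 6-month drop-out figure, so the number above 60 is unknown.

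Finally, the rule covers BMD loss only. SUSAR reporting (Section 5.3) and six-monthly dental screening (Section 5.2) run separately and are not affected.

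**Conclusion.** The contradiction is real and lies within a single section: the event and denominator are at 6 months, while the application is at 1 year. If the 1-year wording governs, every look comes 6 months after the event is known, and the first look has 60–77% of patients enrolled instead of 30–47% across the scenarios tried. Whether patients lost after their 6-month scan would be counted is unclear under that wording, and the direction of any resulting bias is not known.

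The sizes assume uniform accrual at the planned rate with no pause before a look. The statement about which looks fall at or after the end of accrual also assumes follow-up from enrolment. The full 40% is a first-year figure, so it overstates loss by 6 months; the 0 and 40% results bracket the 6-month looks.

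**What to change.** Rewrite the sentence in Section 5.2 so that the timing of the looks matches the event and the denominator: a look each time 10 more patients in an arm have a 6-month BMD, counting every such patient whatever happens afterwards. Remove the reference to 1-year follow-up from this rule.

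List boundaries beyond 60 per arm from the same beta(1,1), 0.95 rule. The stated set matches the 30% threshold, which gives 28/70, 31/80, 35/90, 38/100. The mismatch between 30% in words and 20% in the formula is a separate fault; it must be reconciled first, because the extension depends on it.

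The cost is protocol wording and a short table. The 6-month DEXA is already scheduled for all patients, so no visit or scan is added. Looks would need 6-month BMD data to be available to the monitoring statistician as they accrue.

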2.0 Background

Bone marrow transplantation (BMT) is performed with increasing frequency and for expanding indications, with the majority of patients surviving for many years. In this context, bone loss is a common and serious post-transplant complication. Bone loss, occurs early and most rapidly during the first three to six months after the transplantation, and is often more severe at the femoral neck (1, 2). The degree of bone loss can be severe enough to cause fractures. Lower

bone mineral density in femoral neck in this population has also been associated with avascular osteonecrosis (3).

Osteoporosis developed after BMT has a complex mechanism involving both the direct effect of the transplanted bone marrow on the stromal cell compartment and the effects from immunosuppressive therapies (3). As a result of the decreased osteoblast and increased osteoclast activity, there is both increased bone resorption and decreased bone formation. After the transplantation, over 50% of BMT patients develop some form of Graft Versus Host Disease (GVHD), which requires prolonged use of glucocorticoid as well as other forms of immunosuppression. In addition, BMT recipients may also experience some bone loss before the transplantation (4), that is related to their underlying disease and the modalities used to treat them. Their prior treatment may result in a variety of effects associated with bone loss, including glucocorticoid-induced decreases in bone formation and serum 1,25-dihydroxyvitamin D₃, or chemotherapy-induced hypogonadism. Therefore patients with hematologic malignancies or hematological disorders undergoing bone marrow transplantation are at high risk of bone loss.

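### The safety rule lets a control-arm bone loss close to the one the plan assumes stop the whole trial, and the 80% power ignores it

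*Combined protocol and SAP*

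**What the plan says.** Section 5.2 defines the monitored event as "the percent reduction in BMD is greater than or equal to 15% from baseline to 6 months". With a beta(1, 1) prior for each arm, it prints boundaries of 6/10, 10/20, 14/30, 17/40, 21/50 and 24/60, and then: "The trial will be stopped if for any one of the two arms" the observed fraction reaches its boundary. Control is not exempt and the arms are not compared with each other.

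Section 5.0 sizes the trial on BMD change at 12 months: "Assuming that the mean Diff_BMD is 12% decrease in the control group and is 0.1% in the treatment (Ibandronate) group", "assuming a common standard deviation of 0.23". It claims "80% power to detect this difference at a two-sided significance level of 0.05" with 60 evaluable patients per arm. Two efficacy looks are planned, at 40 and 80 patients followed for one year, with cut-offs of 3.71 and 2.51. The power statement does not mention the safety rule, and no operating characteristics are given for that rule.

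Section 2.0 says that bone loss "occurs early and most rapidly during the first three to six months after the transplantation".

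Section 5.2 also disagrees with itself twice. The limit on the event probability is 30% in words and 20% in the formula. Patients are evaluated after one year in one clause and at 6 months in another.

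**The concern.** The rule monitors an early, dichotomised version of the primary outcome. Bone loss in untreated patients is the premise of the trial, so a control-arm crossing is what the premise predicts. It carries no information about harm from ibandronate. Under a rule that stops on either arm, the more clearly the premise holds, the more likely the trial is to close before its comparison is made. If that probability is material, the stated power is not the power of the design as written.

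**Working it through.** **Plan's own figures.** With a difference of 12 − 0.1 = 11.9 points and an SD of 23 points, n per arm = 2 × (1.96 + 0.842)² × (23/11.9)² ≈ 58.6, so 59. With 60 per arm the power is 80.9% (80.3% by noncentral t). Allowing 40% drop-out, 120/0.6 = 200. The stated size reproduces.

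**Boundaries.** The smallest count r with Prob(p > p₀ | Beta(1 + r, 1 + n − r)) > 0.95 at n = 10, 20, …, 60 is:
- p₀ = 30%: 6, 10, 14, 17, 21, 24, exactly the printed set.
- p₀ = 20%: 5, 7, 10, 13, 15, 17.

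The printed boundaries are used below.

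**Event rates.** Assume that the 12-month means and SD apply at 6 months and that losses are Normal.
- Control: 1 − Φ((15 − 12)/23) = 1 − Φ(0.130) = 0.448.
- Ibandronate: 1 − Φ((15 − 0.1)/23) = 1 − Φ(0.648) = 0.259.

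**Chance of crossing.** An exact sequential binomial calculation, before any efficacy stop, gives these cumulative probabilities:

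| Evaluated per arm | 10 | 20 | 30 | 40 | 50 | 60 |
|---|---|---|---|---|---|---|
| Control | 26% | 45% | 58% | 73% | 79% | 86% |
| Ibandronate | 2% | 3% | 4% | 5% | 5% | 5% |
| Either | 28% | 47% | 59% | 74% | 80% | 87% |

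**Power with the rule binding.** Simulated with 60 per arm, efficacy looks at 20 and 40 per arm using the plan's cut-offs, safety looks every 10 per arm, and a 12-month SD of 23 points throughout. Three inputs are assumptions: a final cut-off near 1.99 (the plan gives only the interim values), a 6- to 12-month correlation of 0.8, and a safety stop counted as no efficacy result. Without the safety rule, power is about 80%. With it, the lower figure in each range takes the safety look first and the higher takes the efficacy look first:

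| 6-month control mean loss | 6-month SD (points) | Power |
|---|---|---|
| 12% | 23 | about 12–22% |
| 9% | 23 | about 30–40% |
| 6% | 23 | about 51–59% |
| 12% | 10 | about 38–47% |
| 12% | 5 | about 74–76% |
| 9% | 10 | about 74–76% |
| 6% | 10 | about 80% |

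If only the ibandronate arm can stop the trial, power at the first row's inputs is about 77–80%.

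**The 20% limit.** With the boundaries that the formula implies, the first row's inputs give an either-arm crossing in more than 99% of trials, and the ibandronate arm alone crosses in about 49%.

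**The case against.** The strongest reply is that the plan's 12% and SD of 23 points describe 12 months, while the event is read at 6. Section 2.0 says that loss is fastest early, not that it is complete by 6 months. The SD was chosen to compare means, and nothing says that it describes the 6-month tail. Taken literally, it has 26% of ibandronate patients losing 15% or more. This stands. A reader might infer that the planning assumptions and the stopping rule cannot both hold, or that the trial is bound to stop. The documents do not support either. With a 6% control mean and an SD of 23 points, either arm crosses in about 38% of trials, and with a 12% mean and an SD of 5 points in about 8%.

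Second, a safety stop need not discard data. At 10 patients a month and 60% evaluable, 60 evaluable patients (30 per arm) need 60/0.6 = 100 enrolled, or month 10. A one-year evaluation puts that third look near month 22, after the 20-month accrual has ended. If crossings from that look on were still followed by a full analysis, face-value power would be about 40%. That is better than 12% but still half the claim, and the plan describes no such analysis. On the 6-month reading the same look falls near month 16, with accrual still open.

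Third, the rule names either arm more than once, so monitoring controls looks deliberate. A limit on severe loss in untreated patients is a legitimate protective aim. That also stands, and it is a reason to keep a control-arm trigger. It does not justify leaving the rule out of the power statement or making the trigger an automatic stop.

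**Conclusion.** The point holds in conditional form. The 80% power is calculated as if the safety rule did not exist. On the plan's own figures taken at face value at 6 months, which the statement about early loss makes plausible but does not establish, the control arm would stop most trials and power would be about 12–22%. A reader might take 12% as the power of the design. It is only the end of the range with the safety look first, and the documents do not state the order of looks. The shortfall remains material at a 6-month control mean of 6% with the plan's SD (about 51–59%), and at a mean of 12% with an SD of 10 points (about 38–47%). It largely disappears only where the 6-month SD is far below the 23 points that produce the sample size. The results rest on Normal losses, the printed boundaries, and the assumptions listed with the simulation.

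**What to change.** 1. Reconcile section 5.2 first: 30% (words and printed boundaries) against 20% (formula), and 6-month against 1-year evaluation. The operating characteristics depend on both, including the 77–80% figure, which holds only for the printed boundaries.
2. Make a control-arm crossing trigger review of the comparative data against the efficacy boundary, in place of an automatic stop.
3. Keep an absolute boundary as an automatic stop for the ibandronate arm. A purely comparative rule is a trade-off, not a like-for-like replacement. For example, stopping when there is more than 95% probability that the ibandronate event rate exceeds control stops only about 14% of trials when the arms are equal, and it drops the absolute limit.
4. State the order of the safety and efficacy looks.
5. Restate power with the retained rule binding, under stated 6-month means, SD and correlation, with a sensitivity range.

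The cost is protocol wording and a short simulation, with no change to visits or sample size. The downside is that a large loss in controls leads to review instead of an automatic stop.
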